1.4 Benefit/risk and ethical assessment

Benralizumab is being studied in severe asthma where there are few treatment options for patients whose asthma remains uncontrolled on high dose ICS/LABA and oral corticosteroids (GINA 2016). In adult patients whose asthma was poorly controlled on medium-to-high dose ICS/LABA therapy, benralizumab at doses of ≥ 20 mg produced improvements in multiple

metrics of asthma control including the annual rate of asthma exacerbations, lung function, ACQ-6 scores, and symptoms ([Castro et al 2014](#)).

Development of anti-drug antibodies (ADA) to benralizumab has been documented. Theoretical risks of developing ADA include decreased drug efficacy and hypersensitivity reactions (eg, anaphylaxis or immune complex disease). Eosinophils are a prominent feature of the inflammatory response to helminthic parasitic infections and the presence of infiltrating eosinophils has been circumstantially associated with a positive prognosis in certain solid tumors. Therefore, there is a theoretical risk that prolonged eosinophil depletion may diminish the ability to defend against helminthic parasites, or negatively impact the natural history of certain malignant tumors. Risk minimization measures herein include exclusion of patients with untreated parasitic infection and active or recent malignancy, in conjunction with the performance of routine pharmacovigilance activities.

The efficacy and safety data obtained to date support the continued clinical development of benralizumab in patients with asthma.

A detailed assessment of the overall risk/benefit of benralizumab is given in the Investigator's Brochure.

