3.2 Exclusion criteria

Subjects should not enter the study if any of the following exclusion criteria are fulfilled:

1. Clinically important pulmonary disease other than asthma (eg, active lung infection, COPD, bronchiectasis, pulmonary fibrosis, cystic fibrosis, hypoventilation syndrome associated with obesity, lung cancer, alpha 1 anti-trypsin deficiency, and primary ciliary dyskinesia) or ever been diagnosed with pulmonary or systemic disease, other than asthma, that are associated with elevated peripheral eosinophil counts (eg, allergic bronchopulmonary aspergillosis/mycosis, Churg-Strauss syndrome, hypereosinophilic syndrome)
2. Life-threatening asthma defined as episodes requiring intubation associated with hypercapnia, respiratory arrest, hypoxic seizures, or asthma related syncopal episodes within the 12 months prior to Visit 1.
3. Acute upper or lower respiratory infections requiring antibiotics or antiviral medication within 30 days prior to the date informed consent is obtained or during the screening/run-in period
4. An upper respiratory tract infection or an asthma exacerbation that required treatment with systemic corticosteroids or an increase in regular maintenance dose of OCS during the screening/run-in period prior to randomization Visit 4
5. Any disorder, including, but not limited to, cardiovascular, gastrointestinal, hepatic, renal, neurological, musculoskeletal, infectious, endocrine, metabolic, haematological, psychiatric, or major physical impairment that is not stable in the opinion of the Investigator and could:
 - Affect the safety of the patient throughout the study

- Influence the findings of the studies or their interpretations
 - Impede the patient's ability to complete the entire duration of study
6. Known history of allergy or reaction to any component of the investigational product formulation
 7. History of anaphylaxis to any biologic therapy
 8. History of Guillain-Barré syndrome
 9. A helminth parasitic infection diagnosed within 24 weeks prior to the date informed consent is obtained that has not been treated with, or has failed to respond to standard of care therapy

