3.10 Discontinuation of investigational product

Subjects may be discontinued from investigational product (IP) in the following situations:

- (a) Patient decision. The patient is free to discontinue treatment at any time, without prejudice to further treatment (see Section 3.10.1)
- (b) Adverse event (AE) that in the opinion of the Investigator contraindicates further dosing
- (c) Risk to patient as judged by the Investigator or AstraZeneca
- (d) Pregnancy

- (e) Lost to follow-up¹
- (f) Severe non-compliance to the study protocol
- (g) Development of any study specific criteria for discontinuation
 - Anaphylactic reaction to the investigational product requiring administration of epinephrine
 - Development of helminth parasitic infestations requiring hospitalization
 - An asthma-related event requiring mechanical ventilation

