6.6.1 Maternal exposure

If a subject becomes pregnant during the course of the study investigational product should be discontinued immediately.

Pregnancy itself is not regarded as an adverse event unless there is a suspicion that the investigational product under study may have interfered with the effectiveness of a contraceptive medication. Congenital abnormalities/birth defects and spontaneous miscarriages should be reported and handled as SAEs. Elective abortions without complications should not be handled as AEs. The outcome of all pregnancies (spontaneous miscarriage, elective termination, ectopic pregnancy, normal birth or congenital abnormality) should be followed up and documented even if the subject was discontinued from the study.

If any pregnancy occurs in the course of the study, then the Investigator or other site personnel informs the appropriate AstraZeneca representatives within 1 day ie, immediately but **no later than 24 hours** of when he or she becomes aware of it.

The designated AstraZeneca representative works with the Investigator to ensure that all relevant information is provided to the AstraZeneca Patient Safety data entry site within 1 or 5 calendar days for SAEs (see Section 6.4) and within 30 days for all other pregnancies.

The same timelines apply when outcome information is available.

The PREGREP module in the CRF is used to report the pregnancy and the PREGOUT is used to report the outcome of the pregnancy.

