### **2.2.1 Important protocol deviations**

Important deviations will be those which are considered to potentially impact upon the interpretation of the primary endpoint in the study. Only important protocol deviations will be listed and tabulated in the CSR.

The following categories of protocol deviations will be reviewed by medical advisors and statisticians prior to database lock to determine those which are considered important deviations as outlined below, with additional details provided in [Appendix 8.3](#):

- Patients who do not meet key inclusion criteria (patients incorrectly randomised)
- Patients who meet any of the key exclusion criteria (patients incorrectly randomised)
- Patients who developed IP discontinuation criteria during the study but were not discontinued
- Patients who received prohibited/restricted concomitant medication(s)
- Deviations from study procedures

Patients for whom significant protocol deviations were recorded that impact the interpretation of the study safety outcomes will have a footnote added to applicable output to describe the deviation and its potential impact. Such patients will be identified as part of the protocol deviation review process prior to database lock.

Patients who received incorrect study treatment will be identified after database lock and unblinding. Patients will be classified according to the treatment they actually received for the safety analysis set according to the following rules, based on the unblinded data from the Interactive Voice Response System (IVRS) system:

- Patients assigned to benralizumab treatment regimen who receive only placebo will be assigned to the placebo group.
- Patients assigned to the placebo group who received 1 or more doses of benralizumab will be assigned to the benralizumab group.

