A summary of reasons for patients withdrawing from the benralizumab treatment arm and the corresponding treatment arm used to calculate the imputation under MAR, and DRMI is given in Table 1.

Reason for withdrawal	MAR	DRMI
Adverse Event	Benralizumab	Placebo
Development of study-specific discontinuation criteria*	Benralizumab	Placebo
Death	Benralizumab	Placebo
Severe non-compliance to protocol	Benralizumab	Placebo
Eligibility criteria not fulfilled	Benralizumab	Benralizumab
Patient lost to follow up	Benralizumab	Benralizumab
Patient decision	Benralizumab	Based on review prior to study unblinding
Other	Benralizumab	Based on review prior to study unblinding

\*Development of study-specific discontinuation criteria are based on the following: anaphylactic reaction to the IP requiring administration of epinephrine, development of helminth parasitic infestations requiring hospitalization, 2 consecutive doses of IP missed or more than 2 scheduled doses of IP are missed during course of the study, an asthma-related event requiring mechanical ventilation.

Together with the primary analysis, the sensitivity analyses are considered to cover the range from realistic to plausible worst case assumptions about missing data. The MAR multiple imputation approach is expected to correspond closely to the primary analysis, and is included to allow for comparisons with MNAR assumptions (specifically methods b) using the same multiple imputation methodology.

The dropout reason-based multiple imputation (DRMI) approach was selected as the most conservative approach based on the fact that placebo patients are receiving standard of care and are not expected to change to a substantially more effective treatment after withdrawing from study or study treatment. For patients receiving benralizumab who withdraw from the study due to treatment related reasons, it is assumed that, at worst, they would be on the standard of care treatment, ie, the placebo arm. For patients receiving benralizumab who withdraw from the study due to non-treatment related reasons, it seems reasonable to assume they would be similar to those patients who complete treatment.

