#### *Overall summary of analyses to account for missing data*

A summary of the different analyses to be carried out under different estimands and assumptions are described in Table 3.

Treatment Policy Estimand			
	DL	MAR	DRMI
Population	On-treatment + post-discontinuation of randomized treatment		
Estimand	Treatment policy (MAR)	Treatment policy (MNAR)	
Imputation of pre-BD FEV1 in Benra arm	No explicit imputation*	Benra rate assumed for all reasons for withdrawal	Placebo rate assumed for AEs, Death, development of study specified reasons to stop active treatments and Severe non-compliance to protocol, otherwise Benra or based on review prior to study unblinding.

\* Implicitly assumes unobserved data the same as observed

Forest plots will be used to show the primary and sensitivity analysis under the different estimands.

It is noted that if the primary analysis is statistically significant, it is not necessarily expected that all sensitivity analyses will also give statistically significant results. If the results of the sensitivity analyses provide reasonably similar estimates of the treatment effect to the primary analysis, this will be interpreted as providing assurance that neither the lost information nor the mechanisms which cause the data to be missing have an important effect on primary analysis conclusions. Based on these outputs and the drug's mechanism of action, the plausibility of the assumptions made about missing data in the different analyses will be considered and described in the clinical study report.

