**E. Discontinuation and withdrawal**

1. Subject met IP discontinuation criteria but was not discontinued from IP

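### Protocol 3.10 words the stop after anaphylaxis to the product as optional, while the SAP counts failure to stop as an important deviation

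*Protocol*

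**What the plan says.** **Protocol, stopping.** Section 3.10 introduces items (a) to (g) with "Subjects may be discontinued from investigational product (IP) in the following situations". Item (g) is labelled as the study-specific discontinuation criteria and names the three events: anaphylaxis to the product treated with epinephrine, a helminth infestation leading to hospital admission, and an asthma event requiring ventilation. Pregnancy is item (d) of the same list, but 6.6.1 adds that "investigational product should be discontinued immediately", and 7.2 allows a dose only after a negative urine test.

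**Protocol, entry.** Exclusion criterion 7 in 3.2 is "History of anaphylaxis to any biologic therapy".

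**Protocol, after a stop.** Section 3.10.1 removes from the study a patient who receives dose 1 and misses both doses 2 and 3. Its next paragraph asks that patients who stop the product be encouraged to complete all remaining visits. Those unwilling to continue after the premature-discontinuation (IPD) visit are asked back 8 weeks after their last dose. Section 8.5 relies on assessments continuing after treatment stops.

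**SAP.** Section 2.2.1 lists, among the deviation categories to be reviewed before database lock, "Patients who developed IP discontinuation criteria during the study but were not discontinued". Section 8.3 E.1 lists as an important deviation "Subject met IP discontinuation criteria but was not discontinued from IP". In 8.1, the footnote to the table of withdrawal reasons defines the study-specific criteria as "anaphylactic reaction to the IP requiring administration of epinephrine, development of helminth parasitic infestations requiring hospitalization", together with missed-dose rules and the ventilation event. The later summary table in 8.1 speaks of "development of study specified reasons to stop active treatments".

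**The concern.** A site that gives another dose after an epinephrine-treated reaction to this product has followed the wording of 3.10, yet would be recorded under SAP 8.3 E.1 as an important deviation. One verb covers both matters where nobody exercises discretion (patient decision, loss to follow-up) and safety events where a firm rule would be expected. Anaphylaxis is the clearest case. A past reaction to any biologic bars entry, and protocol 1.4 names anaphylaxis among the theoretical risks of anti-drug antibodies, but a reaction to this product does not, in terms, bar the next dose.

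There is a second-order problem. Making the stop mandatory after dose 1 means that doses 2 and 3 are both missed, which triggers the exit rule in 3.10.1. Without a companion change, a safety correction would cut short adverse event and FEV₁ collection in the patients who most need follow-up.

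**Working it through.** The plan gives no figure on this point, so the main check is a comparison of texts.

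**1. Is there a mandatory stop or a bar on re-dosing elsewhere in the protocol?**

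| Place | What it does | Mandatory stop for a (g) event? |
|---|---|---|
| 3.10 (b), (c) | Investigator or sponsor may stop for an adverse event or risk | No, discretionary |
| 3.10.1 | Procedures after a stop; missed doses | No |
| 6.6.1 | Directs a stop for pregnancy | Pregnancy only |
| 6.7, Appendix D | Recognition, treatment, observation and sampling for anaphylaxis | No |
| 7.2, pre-dose checks | Injection site; urine pregnancy test | No check for an earlier event |
| 7.2, rescheduling | Postpones a dose for unsafe intercurrent illness, acute exacerbation or fever | No, the hold ends at the rescheduled visit |
| Appendix A | Remark in the causality guide that the sponsor normally does not favour re-challenge | No, hedged |

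Mandatory stop in the protocol: 0 of the 3 criteria in 3.10(g). All 3 are named as discontinuation criteria in the SAP 8.1 footnote, which also adds missed-dose criteria that 3.10(g) does not contain. Only 1 of the 3 (anaphylaxis) has a close entry counterpart. Exclusion 9 concerns helminth infection that is untreated or unresponsive, and exclusion 2 concerns defined life-threatening episodes within 12 months.

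**2. Doses left open by the wording.** Three doses are planned (Days 0, 28, 56). Further doses = 3 − number already given: 2 after dose 1, 1 after dose 2, 0 after dose 3.

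**3. What the exit rule would cost a patient stopped after dose 1.** The primary contrast uses Days 28, 56 and 84; planned follow-up runs to Day 112, which is 16 weeks.

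- *Exit applied at the IPD visit* (about 4 weeks after dose 1, standing in for Day 28): Days 56 and 84 are lost, 2 of 3 visits. Follow-up is 4/16 = 25% of plan.
- *Exit applied once the second missed dose is established, at Day 56*: only Day 84 is lost, 1 of 3. Follow-up is 8/16 = 50%.
- *Exit at the IPD visit plus the 8-week visit in 3.10.1* (written for patients unwilling to continue): follow-up is again 8/16 = 50%. Eight weeks after dose 1 is study day 57. SAP Table 1 places that in the Day 56 window (study days 43 to 70), so spirometry done then would leave only Day 84 lost.

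**4. Effect on the primary estimate.** Inputs: assumed average difference 138 mL and 115 patients per arm (protocol 8.2). Assumption: the lost values of one benralizumab patient would have been fully placebo-like, while the model treats them as typical of the arm. Shift per lost visit = 138/115 = 1.2 mL at that visit. Averaged over three visits:

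- two lost: 1.2 × 2/3 = 0.8 mL, or 0.8/138 ≈ 0.6%
- one lost: 1.2 × 1/3 = 0.4 mL, or about 0.3%

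The documents give no rate for these events, so no expected number of such patients can be derived.

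**The case against.** The best reply is that *may* in 3.10 only introduces a list of grounds. It also governs patient decision and loss to follow-up, where permission makes no sense, and item (g) is itself labelled as discontinuation criteria. On that reading protocol and SAP agree, and the defect is one of drafting. This is plausible and limits the point, but the operative verb is still permissive and pregnancy was given a separate directive.

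Several safeguards also stand. Appendix A leans against re-challenge. Under 3.10(b) and (c) the Investigator or sponsor can stop, and 6.4 brings serious events to the sponsor within 24 hours. The Investigator's Brochure and the IP Handling Instruction, which 7.2 makes binding for administration, are not among the documents and may contain a bar. A reader might infer that the protocol invites re-dosing after anaphylaxis and that nothing speaks against it; these provisions do not support that.

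The SAP evidence should not be over-read either. The 8.1 tables classify withdrawal reasons for imputation and do not say that stopping is compulsory. The mismatch rests on 2.2.1 and 8.3 E.1.

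Finally, a compulsory permanent stop after a resolved helminth or ventilation event removes clinical judgement. For those two, the case rests only on the label in 3.10(g) and the SAP deviation rule.

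**Conclusion.** The point holds as a minor mismatch. The protocol leaves stopping after a 3.10(g) event to discretion in its wording, and the SAP counts not stopping as an important deviation. It is strongest for anaphylaxis. Re-dosing is unlikely in practice and the effect on the primary estimate is negligible, so the reasons to act are patient safety and agreement between the documents, not bias.

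The exit rule in 3.10.1 conflicts with its own next paragraph, with 8.5 and with the treatment-policy estimand in SAP 8.1. Its cost is one or two of the three contrast visits, with follow-up ending about 4 to 8 weeks after dose 1 instead of at 16.

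Two stronger readings are not supported. One is that such a patient always loses two visits and 75% of follow-up; that requires exit at about Day 28 with no further visit. The other is that follow-up should be judged against 16 weeks as five half-lives. The protocol uses that interval for contraception, donation and vaccine restrictions, and a completer last dosed at Day 56 is seen only 8 weeks later, at Day 112.

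The conclusion assumes that the SAP's discontinuation criteria include the 3.10(g) events, as the 8.1 footnote indicates, and that no unseen document already bars re-dosing.

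**What to change.** 1. **Protocol 3.10.** State that the product must be permanently discontinued for pregnancy and for anaphylaxis to it that needs epinephrine. For the helminth and ventilation criteria, either make the stop mandatory as well, which matches the SAP, or require documented sponsor agreement before any further dose. Keep *may* for (a), (b), (c), (e) and (f).
2. **Protocol 7.2.** Add to the checks before each dose a confirmation that none of these criteria has occurred. If one has, no dose is given unless the sponsor-agreement route applies.
3. **Protocol 3.10.1.** State that a patient stopped for these reasons stays in the study for all visits to Day 112 and is not removed by the rule on missing both the 2nd and 3rd dose.

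The cost is one protocol amendment of a few sentences. No assessments are added, since these patients attend visits already scheduled. SAP 8.3 E.1 can stay as it is if all three stops become mandatory. Under the sponsor-agreement route, it should be made clear that an agreed continuation is not a failure to stop. The downside is some loss of Investigator discretion, mainly after a resolved helminth or ventilation event.

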3.10.1 Procedures for discontinuation of a subject from investigational product

At any time, subjects are free to discontinue investigational product or withdraw from the study (ie, investigational product and assessments – see Section 3.11), without prejudice to further treatment. A subject that decides to discontinue investigational should always be asked about the reason(s) and the presence of any adverse events.

All patients must be administered the first dose of IP. If the patient misses the first IP administration they must be discontinued from the study and should return for IPD visit. If the patient receives the first IP administration but misses both the 2nd and the 3rd dose they must be discontinued from the study and should return for the IPD visit. If the patient receives the first IP administration but misses either the 2nd or 3rd dose they need not discontinue from the study

All patients who prematurely discontinue investigational product should return to the study center and complete the procedures described for the premature IP Discontinuation (IPD) visit within 4 weeks \pm 3 days after the last dose of IP. At that visit, although no longer on IP, patients should be encouraged to remain in the study to complete all subsequent study visits, procedures, and assessments. Note that in this case, the IPD visit replaces the nearest regular visit while the following visits continue as possible

If the patient is not willing to participate further in the study after the IPD visit, the patient should still return for a follow up visit 8 weeks \pm 3 days after the last dose of IP for final study-related assessments.

The reasons for premature discontinuation of IP should be recorded in the eCRF.

¹ Patient is considered lost to follow up when any of the following attempts of contact are failed: 3 attempts of either phone calls, faxes or emails; having sent 1 registered letter/certified mail; or 1 unsuccessful effort to check the vital status of the patient using publicly available sources, if allowed by local regulations.

If a subject is withdrawn from study, see Section 3.11.

